# Create a contingency table
                        pd.crosstab(tabla1['BDD'],
contingency_table
tabla1['Female'])
# Calculate the chi-squared test
chi2, p, _, _ = chi2_contingency(contingency_table)
# Calculate the ratio of Male to Female in the positive BDD
group
positive_BDD_female = tabla1[(tabla1['BDD'] ==
                                                     1)
                                                          &
(tabla1['Female'] == 1)].shape[0]
                       tabla1[(tabla1['BDD']
positive_BDD_male =
                                                     1)
                                                          &
(tabla1['Male'] == 1)].shape[0]
```

```
ratio_male_to_female_positive_BDD = positive_BDD_male
positive_BDD_female
# Calculate the ratio of Male to Female in the negative BDD
group
negative_BDD_female = tabla1[(tabla1['BDD'] ==
                                                      0)
                                                           &
(tabla1['Female'] == 1)].shape[0]
negative_BDD_male =
                        tabla1[(tabla1['BDD']
                                                     0)
                                                           &
(tabla1['Male'] == 1)].shape[0]
ratio_male_to_female_negative_BDD = negative_BDD_male
                                                           /
negative_BDD_female
# Calculate the relative risk
relative_risk = (positive_BDD_male / positive_BDD_female) /
(negative_BDD_male / negative_BDD_female)
```

Outcome Analysis:

 Patient satisfaction levels as measured by the Visual Analog Scale (VAS).

Data Analysis:

Data analysis will be performed using Python in a Colab environment.
 The analysis will focus on correlations between BDD and identified risk factors, chi-square tests for gender differences, as well as the effectiveness of the AI model in screening for BDD.

Access Instructions: To request permission to access the individual participant data (IPD) and supporting information, please email [contact]. Detailed instructions for requesting access can be found at IPD Sharing Instructions.

Conclusion: This SAP provides a detailed plan for the statistical analysis of the study "Artificial Intelligence Screening for Body Dysmorphic Disorder in Aesthetic Surgery: Improving Patient Safety and Outcomes." The analysis aims to provide insights into the effectiveness of the AI model in identifying and managing patients at risk for BDD, ultimately improving surgical outcomes and patient safety.

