Participants will undergo a screening assessment using the Al model, which evaluates multiple factors based on their responses to the BDDQ and additional psychological data. The Al model will generate risk scores and recommendations for psychological referral if necessary.

Follow-Up

The follow-up period for this study ranges from 1 to 43 months post-surgery, with a mean follow-up of 22 months. Data on patient satisfaction and surgical outcomes will be collected and analyzed.

Outcome Measures

Primary Outcome Measure

- Title: Patient Satisfaction Post-Surgery
- **Description:** The primary outcome measure is the level of patient satisfaction with the cosmetic surgery results, measured using the Visual Analog Scale (VAS) within the follow-up period after surgery.

Secondary Outcome Measure

- Title: Correlation Between Positive BDD Screening and Risk Factors
- Description: This measure evaluates the correlation between a positive Body Dysmorphic Disorder (BDD) screening result and various risk factors, including demographic factors (age, gender), psychological stress levels, and previous psychiatric history. The study will utilize chi-square tests to analyze gender differences in the prevalence of BDD among the patient population.

The goal is to identify patterns that could inform better patient selection and management in cosmetic surgery.

Conclusion

This study protocol provides a comprehensive overview of the study design, objectives, data collection methods, and outcome measures for the observational study "Artificial Intelligence Screening for Body Dysmorphic Disorder in Aesthetic Surgery: Improving Patient Safety and Outcomes." The integration of Al-powered screening is expected to improve patient selection, surgical planning, and overall outcomes in aesthetic surgery.

Statistical Analysis Plan (SAP)

Introduction: This Statistical Analysis Plan (SAP) outlines the statistical methods and analyses to be performed for the study titled "Artificial Intelligence Screening for Body Dysmorphic Disorder in Aesthetic Surgery: Improving Patient Safety and Outcomes." The primary aim of the study is to assess the effectiveness of the Al-powered screening tool in identifying patients at risk for BDD and its impact on surgical decision-making.

Study Objectives:

- To evaluate the effectiveness of the Al-based screening tool in identifying patients at risk for BDD.

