# Correlation calculations
stats.pearsonr(corr4['BDD'], corr4['Age'])
stats.pearsonr(corr4['BDD'], corr4['Stress in the last 3
months'])
stats.pearsonr(corr4['BDD'], corr4['Male'])
stats.pearsonr(corr4['BDD'], corr4['Female'])
```

• Chi-Square Analysis:

 Chi-square tests will be conducted to evaluate the differences in the prevalence of BDD between genders, helping to identify any statistically significant associations between gender and BDD.

Python code

```
from scipy.stats import chi2_contingency

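### The SAP code labels an odds ratio as a relative risk, which overstates any gender difference in BDD positivity when positivity is not rare

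*Combined protocol and SAP*

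**What the plan says.** The protocol's secondary outcome includes a comparison of BDD positivity between men and women, framed in terms of prevalence: "The study will utilize chi-square tests to analyze gender differences in the prevalence of BDD among the patient population". The SAP's Chi-Square Analysis section repeats that framing: "Chi-square tests will be conducted to evaluate the differences in the prevalence of BDD between genders".

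The code in that section counts the four cells of the BDD-by-gender table (each count ends in a selection such as "tabla1['Male'] == 1)].shape[0"). It then forms male-to-female ratios within each BDD group. For the negative group, the comment reads "Calculate the ratio of Male to Female in the negative BDD" and the line begins "ratio_male_to_female_negative_BDD = negative_BDD_male". The final step, under the comment "Calculate the relative risk", sets "relative_risk = (positive_BDD_male / positive_BDD_female" over "negative_BDD_male / negative_BDD_female".

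Neither document uses the term odds ratio, appeals to a rare-outcome approximation, or describes recruiting patients according to BDD status. Neither gives an expected positive rate, a sample size or a gender split.

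**The concern.** The name and the quantity do not match. The code compares the gender mix of positives with the gender mix of negatives. A relative risk compares the chance of a positive screen between the genders. The study enrols patients prospectively without selecting on BDD status, so prevalence by gender can be estimated directly and nothing in the design forces the use of odds.

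This is the only ratio measure of the gender contrast in the SAP; the other gender results are a chi-square test and Pearson coefficients. A reader who wants to know how much more often one gender screens positive would naturally turn to it, and would read a value of X as men being X times as likely to screen positive. If positivity differs by gender and is not rare, that reading exaggerates the difference. The secondary outcome is meant to inform patient selection, so the size of the contrast matters as well as its p-value.

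**Working it through.** **Inputs.** From the SAP code: M+ and F+ are the numbers of men and women screening positive, and M− and F− the numbers screening negative. The documents state no numerical result to reproduce, so the check is algebraic, followed by an illustration under assumed rates.

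**Step 1: what the code computes.**

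(M+ / F+) ÷ (M− / F−) = (M+ × F−) / (F+ × M−)

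This is the odds ratio (OR). A check in exact fractions on 20,000 random 2×2 tables gave equality in all 20,000.

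**Step 2: what a relative risk is.**

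RR = [M+ / (M+ + M−)] ÷ [F+ / (F+ + F−)]

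This needs the gender totals, and none enters the ratio calculation in the code. (The chi-square function uses the table margins internally, but that does not feed into the ratio.)

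**Step 3: how the two relate.** Write pM and pF for the proportions positive in men and women. Then

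OR = [pM / (1 − pM)] ÷ [pF / (1 − pF)] = RR × (1 − pF) / (1 − pM)

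If pM > pF the multiplier exceeds 1, and if pM < pF it is below 1. The code value therefore lies on the same side of 1 as the true RR but further away, and the two agree only when pM = pF. In the random tables this held in all 19,998 with RR different from 1.

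**Step 4: size, under assumed rates.** Put pM = RR × pF into the formula. For example, with pF = 0.20 and RR = 2.0, pM = 0.40 and OR = 2.0 × 0.80 / 0.60 = 2.67. The values returned by the code are:

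| Assumed positivity in women | True RR 0.5 | True RR 1.0 | True RR 1.5 | True RR 2.0 |
|---|---|---|---|---|
| 2% | 0.49 | 1.00 | 1.52 | 2.04 |
| 5% | 0.49 | 1.00 | 1.54 | 2.11 |
| 10% | 0.47 | 1.00 | 1.59 | 2.25 |
| 20% | 0.44 | 1.00 | 1.71 | 2.67 |
| 30% | 0.41 | 1.00 | 1.91 | 3.50 |

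For a true RR of 1.5, the code value is 1% too high at 2% positivity and 27% too high at 30%. For a true RR of 2.0, the range is 2% to 75%.

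**Step 5: a hypothetical table.** Suppose 16 of 40 men and 32 of 160 women screen positive.

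- True RR = (16/40) / (32/160) = 0.40 / 0.20 = 2.00. SE(ln RR) = √(1/16 − 1/40 + 1/32 − 1/160) = 0.25, giving a 95% CI of 1.23 to 3.26.
- Code value = (16/32) / (24/128) = 0.500 / 0.1875 = 2.67. As an odds ratio, SE(ln OR) = √(1/16 + 1/32 + 1/24 + 1/128) = 0.378, giving a 95% CI of 1.27 to 5.60.
- Chi-square with the function's default continuity correction, as the SAP code would run it: 5.96, p = 0.015, whichever ratio is reported.

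**The case against.** The term appears only as a code comment and a variable name. The protocol's secondary outcome and the SAP's Chi-Square Analysis and Data Analysis text name chi-square tests and correlations, and none commits to reporting a relative risk. The odds ratio is itself a valid measure of association for a 2×2 table, and the formula is printed in full, so a reader of the SAP can see what it is. The test, the direction of effect and the null value do not change. The larger distortions need high positivity: the 75% figure assumes 30% in women and 60% in men. At 2% positivity the error is only 1% to 2%, and the documents cannot show where this study will fall.

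All of this stands as a limit on the weight of the point, but none of it makes the label correct. The code is the analysis the SAP specifies, so the name would carry into its output, and someone reading a results report would not see the formula. Damage to the text in PDF extraction is not an explanation either. A division sign has dropped out of the earlier line for the positive group, but the final expression is complete.

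**Conclusion.** The concern holds. The quantity called a relative risk is an odds ratio at any prevalence, and this needs no outside figure. The consequence is conditional: the value must be reported under its present name, positivity must differ by gender, and positivity must not be rare. Under the assumed rates, the exaggeration is negligible at about 2% positivity in women and becomes material, in my judgement, from about 10% to 20%. At 20%, the code value is 14% too high for a true RR of 1.5 (1.71/1.5) and 33% too high for a true RR of 2.0 (2.67/2.0). The actual size in this study cannot be stated, because the documents give neither a positive rate nor an expected gender effect. The fault concerns the name and size of a secondary effect measure; the significance test and the primary VAS outcome are not touched. It should be corrected before results are reported.

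**What to change.** Choose one of two equally valid corrections.

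1. Keep the name and change the formula, which matches the stated interest in prevalence: `relative_risk = (positive_BDD_male / (positive_BDD_male + negative_BDD_male)) / (positive_BDD_female / (positive_BDD_female + negative_BDD_female))`.
2. Keep the formula and rename the variable and its comment to odds ratio, using that term in every report of the value.

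Give a 95% confidence interval with whichever measure is kept. That is a separate improvement, not part of correcting the label.

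The cost is one line of code or one label, with no new data. If the first option is taken and positivity differs by gender, the reported ratio will be closer to 1 than the present code would give.

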- To determine the correlation between various demographic and psychological factors (such as age, gender, and stress levels) and positive BDD screening results.
- To assess the impact of early psychological intervention on surgical decision-making and outcomes.

Study Design: This is an observational study with a prospective time perspective. The study involves the collection of psychological and demographic data from patients seeking elective aesthetic surgery. The Al model analyzes this data to identify at-risk patients and provide recommendations for psychological evaluation.

Data Collection: The following data will be collected from each participant:

- Age
- Gender
- Stress levels
- BDDQ scores
- Surgical outcomes (where applicable)
- Patient satisfaction (as measured by the Visual Analog Scale, VAS)

Statistical Methods:

• Descriptive Statistics:

- Frequency and percentage of patients screening positive for BDD.
- Analysis of demographic data and stress factors.

Pearson Correlation:

o Correlation between BDD and factors such as age, gender, and stress.

Python code

```

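### The planned risk-factor analyses take age, stress and gender one at a time, so they cannot show what each adds given the others

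*Combined protocol and SAP*

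**What the plan says.** The protocol's Secondary Outcome Measure asks for the correlation between a positive BDD screen and several factors: age, gender, "psychological stress levels, and previous psychiatric history". It gives the purpose as follows: "The goal is to identify patterns that could inform better patient selection and management in cosmetic surgery".

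The SAP's Pearson Correlation item reads "Correlation between BDD and factors such as age, gender, and stress". Its code makes four separate two-variable calls, for age, stress in the last 3 months, male and female. Under Chi-Square Analysis, "Chi-square tests will be conducted to evaluate the differences in the prevalence of BDD between genders"; the code cross-tabulates BDD by the female indicator, then forms a male-to-female ratio from the same four cells. The Data Analysis section summarises the whole: "The analysis will focus on correlations between BDD and identified risk factors, chi-square tests for gender differences", together with the effectiveness of the AI model.

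The Data Collection lists in the protocol and the SAP both open with "The following data will be collected from each participant" and name the same six items: age, gender, stress levels, BDDQ scores, surgical outcomes and satisfaction. Previous psychiatric history is in neither list.

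**The concern.** Age, gender and stress are to be recorded on every participant. If the results are to guide selection, a natural question is what gender or age says about a patient whose stress level is already known. A crude association answers a different question: how BDD differs between men and women, or across ages, with everything else left to vary. The two answers can differ in size, and sometimes in direction, when stress or age differs by gender. A reader given only the crude results cannot tell which factors carry separate information and which merely accompany another.

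Part of the secondary outcome also cannot be delivered as written, because one named factor is neither collected nor analysed.

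**Working it through.** **Step 1: what is planned.** The documents give no sample size, BDD prevalence, gender mix, stress scale or age distribution, so there is no plan figure to reproduce. The listed analyses can be checked one by one for a second factor.

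- Pearson, BDD with age: none.
- Pearson, BDD with stress: none.
- Pearson, BDD with male, and BDD with female: none (and if the two indicators are complementary, these give the same result with opposite sign).
- Chi-square, BDD by female: none.
- Male-to-female ratio: none. It is (positive men / positive women) / (negative men / negative women), which is the crude odds ratio (OR), although the code names it a relative risk.

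Analyses containing BDD and two or more of age, stress and gender: 0. No regression, partial correlation or stratification appears in either document.

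**Step 2: how far crude and conditional gender results could differ.** All inputs are assumed: 20% of patients are men; BDD risk in women is 10% unstressed and 30% stressed; 50% of women and 30% of men are stressed.

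*No gender difference at equal stress.*
- Women: 0.5 × 0.30 + 0.5 × 0.10 = 0.20.
- Men: 0.3 × 0.30 + 0.7 × 0.10 = 0.16.
- Crude OR: (0.16/0.84) / (0.20/0.80) = 0.76, against 1.00 at equal stress.
- Range: 0.88 if 50% of women and 40% of men are stressed, to 0.58 if 60% and 20% are.

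*Male OR 2 at equal stress.*
- Male risks: odds 2 × 0.1/0.9 give 0.182 unstressed; odds 2 × 0.3/0.7 give 0.462 stressed.
- Men overall: 0.7 × 0.182 + 0.3 × 0.462 = 0.266. Crude OR: (0.266/0.734) / 0.25 = 1.45.
- If 50% of both genders were stressed, men's risk would be 0.322 and the crude OR 1.90. Non-collapsibility therefore explains ln(2/1.897) / ln(2/1.448) = 0.053/0.323, about 16% of the gap.
- Risk differences are collapsible. Crude: 0.266 − 0.200 = 6.6 points. Standardised to the overall 46% stressed (0.8 × 0.5 + 0.2 × 0.3): 0.3105 − 0.192 = 11.8 points.

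*Direction.* Solving for a crude OR of 1 gives a conditional male OR of 1.34, so any conditional OR between 1 and 1.34 shows a crude OR below 1. The limit is 1.15 for the 50 v 40% gap and 1.80 for the 60 v 20% gap.

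**Step 3: age.** Assume age SD 12, women's prevalence 20%, men 7 years younger, BDD OR 0.7 per 10 years, and no gender difference at equal age. Integrating over age gives a crude male/female OR of 1.27 (1.03 for 3 years and OR 0.9; 1.41 for 10 years and OR 0.7).

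The age correlation itself is as open. The partial correlation given stress is (r_BA − r_BS × r_AS) / √[(1 − r_BS²)(1 − r_AS²)]. With assumed r_BA = −0.15 and r_BS = 0.30, it is 0.000 if r_AS = −0.5, −0.157 if r_AS = 0, and −0.264 if r_AS = +0.3. One crude value fits all of these.

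**Step 4: precision cost of adjusting.** In simulation of the first Step 2 setting, the ratio of upper to lower 95% limit for the gender OR is about 7.4 adjusted v 6.6 crude at n = 200, 3.5 v 3.3 at n = 500 and 2.4 v 2.3 at n = 1000.

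**Step 5: what BDD means in the code.** The code uses a column named BDD, which neither document defines as the BDDQ result or the AI result. The protocol's Study Population Description has the AI model analyse the BDDQ together with age, gender and stress. If the column is the AI output, those factors are inputs to the outcome, and any association, crude or adjusted, partly recovers the algorithm's own weights.

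**The case against.** The plan does what it literally says. The second objective and the title of the secondary outcome ask for correlation, and the protocol itself names chi-square for gender. Neither document claims an independent or adjusted risk factor. Selection is described through the AI tool, which already combines several factors, and nothing says that clinicians will select on gender or age coefficients. All of this stands. It makes the point an improvement towards the stated goal rather than a breach of the plan's own aim. The AI score does not fill the gap, because no analysis is described that estimates each factor's contribution to it.

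The practical effect is also unestablished. In the main example, the distance from 0.76 to 1.00 is about 0.57 standard errors of the crude log OR at n = 200 and 1.28 at n = 1000, so a changed conclusion is not shown. That stands too.

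Two stronger readings are tempting. One is that the crude gender test is wrong. The documents do not support that: it is valid for the prevalence question that the SAP puts to it, and if stress is a mediator the crude value is the total gender difference. The other is that the reported associations will be distorted by amounts like those above. Every input there is assumed, and the figures are differences between two questions, not error rates.

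**Conclusion.** The point holds as a modest one, worth considering. The pairwise analyses meet the wording of the objective and are sound for crude questions, but none can show whether age, gender or stress adds information given the others, and that limits what they can contribute to patient selection. Its size here is unknown. Under the assumed stress imbalances, the crude gender OR lies between 0.58 and 0.88 when the conditional OR is 1; with stress and age balanced by gender, only the non-collapsibility part remains. Whether a joint model is feasible depends on the number of positive screens and on how stress is recorded, neither of which is documented.

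The mismatch over previous psychiatric history rests on the text alone and needs no assumption.

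**What to change.** - Keep the crude analyses.
- Define the outcome for all association analyses as the BDDQ screening result, not the AI output. This must come first; regression does not cure an outcome built from its own covariates.
- Add one prespecified logistic regression of that outcome on age, gender and stress in the last 3 months, without stepwise selection. Use a Firth penalised fit if positives are few (for example, under about 10 per coefficient).
- Report crude and adjusted odds ratios with 95% CIs side by side, and for gender the crude and standardised risk differences. State that stress may be a mediator and that odds ratios are non-collapsible.
- Add previous psychiatric history to both data lists and to the association analyses, or remove it from the secondary outcome.

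The cost is a few lines of code on variables already listed, provided that stress is recorded in an analysable form; one extra data item if psychiatric history is kept; and the slightly wider intervals shown in Step 4.

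Two minor, separate points: gender is tested by both Pearson and chi-square, and the continuity setting is not stated in the SAP text (the default for a 2×2 table applies the Yates correction). With invented counts of 10/40 men and 20/160 women, p is 0.048 by Pearson and 0.083 by the default chi-square. One unadjusted gender test with its setting stated is enough.
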